5.5.6. Discontinuation of Mirvetuximab Soravtansine Due to Toxicity

MIRV should be discontinued in the case of the following treatment-related events:

- Grade \geq 3 cardiac event (excluding Grade 3 hypertension) ([Section 5.5.1.1](#))
- Grade \geq 3 pneumonitis event ([Section 5.5.3](#))
- Non-hematologic events of Grade 4 severity ([Section 5.5.1.1](#))
- Ocular events of Grade 4 severity ([Section 5.5.2.2](#))
- Failure to meet re-treatment criteria within 1 cycle (21 days) after the missed dose due to insufficient recovery from a treatment-related toxicity unless otherwise specified in the management guidance for a particular toxicity. In such cases, continuation of MIRV may be considered for those patients who have experienced clinical benefit if agreed upon between the Sponsor and the Investigator.

5.6. Discontinuation of the Patients from the Study or Study Treatment

5.6.1. End of Treatment

Patients will continue to receive MIRV until they present with PD per RECIST 1.1, as assessed by study Investigator, unacceptable toxicity, withdraw consent, or death, whichever comes first, or until the Sponsor terminates the study. Study treatment and/or participation in the study may be discontinued at any time at the discretion of the Investigator. The following may be reasons for the Investigator to remove a patient from the study drug:

- The patient suffers an intolerable AE
- Noncompliance, including failure to appear at one or more study visits
- The patient was erroneously included in the study

The reason for treatment discontinuation must be captured in the clinical trial database. Any AEs experienced up to the point of discontinuation and 30 days thereafter must be documented. All serious adverse events (SAEs), and those AEs assessed by the Investigator as at least possibly related to study drug should continue to be followed until they resolve or stabilize, whichever comes first. Patients will continue to be followed for OS, after discontinuing study drug ([Section 9.3.3](#)).

5.6.2. End of Study

Discontinuation from participation in the study will be documented in the clinical trial database. Reasons for EOS include withdrawal of consent, lost to follow-up, death, or study termination by Sponsor.

5.6.3. Withdrawal of Consent

The patient or legally authorized representative acting on behalf of the patient is free to withdraw consent to study treatment and/or participation in the study at any time irrespective of the reason. The Investigator must make every effort (eg, telephone, email, letter) to determine the primary

reason for this decision and record this information. Study treatment must be discontinued, and no further assessments conducted. Further attempts to contact the patient are not allowed unless safety findings require communication or follow-up. If the patient or legally authorized representative withdraws consent for disclosure of future information, the Sponsor may retain and continue to use any data collected before withdrawal of consent. All biological samples that have been already collected will be retained and analyzed at a later date. The patient or legally authorized representative may request destruction of any samples, and the Investigator must document this in the site study records. The SAP will specify how early withdrawals from treatment will be accounted for in the analyses of efficacy endpoints. Patients who have withdrawn from the study cannot be re-treated in the study and their inclusion and patient number must not be reused.

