5.6.4. Lost to Follow-up

A study patient will be considered lost to follow-up if the patient repeatedly fails to return for scheduled visits and is unable to be contacted by the study site. The Investigator should make all efforts to contact the patient and to determine the patient's health status, including at least her vital status (in accordance with applicable regulations related to privacy and confidentiality). A patient should not be considered lost to follow-up until due diligence has been completed and documented. The following actions must be taken if a patient fails to return to the clinic for a required study visit:

- The site must attempt to contact the patient and reschedule the missed visit as soon as possible and counsel the patient on the importance of maintaining the assigned visit schedule and ascertain whether or not the patient wishes to and/or should continue in the study.
- In cases in which the patient is deemed lost to follow-up, the Investigator or designee must make every effort to regain contact with the patient (where possible, 3 telephone calls and, if necessary, a certified letter to the patient's last known mailing address or local equivalent methods). These contact attempts should be documented in the patient's medical record.

Should the patient continue to be unreachable, he/she will be considered to have withdrawn from the study with a primary reason of lost to follow-up.

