9.2. End of Treatment Visit

Patients may voluntarily withdraw from the study drug at any time for any reason, and without prejudice to further treatment. In addition, patients may be withdrawn by the Investigator if they do not feel the patient is deriving clinical benefit or because the patient is experiencing unacceptable toxicity. The reasons for which a patient may be prematurely discontinued are listed in [Section 5.6](#). The clinical trial database will capture reasons for withdrawal.

Patients who withdraw or are removed from the study treatment will have an EOT visit within 7 days of the decision to discontinue study drug. Patients will undergo assessments as outlined in [Table 2](#).

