9.3.3. Survival Follow-up

All patients who discontinue MIRV for any reason will be followed for survival after disease progression as per Investigator, or after start of a new anticancer therapy. Survival status will be assessed every 3 months (± 1 month) until death, lost to follow-up, withdrawal of consent for survival follow-up or until EOS, whichever comes first. Additional survival follow-up calls may occur periodically if needed.

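### Protocol 5.6.3 does not separate withdrawal from study treatment from withdrawal from the study, and so contradicts the follow-up that 5.6.1 and 9.2 to 9.3.3 require after a patient stops MIRV

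*Protocol*

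**What the plan says.** Section 5.6.3 of the protocol opens by saying that the patient is "free to withdraw consent to study treatment and/or participation in the study at any time irrespective of the reason". It then states the consequence and the contact rule, dividing neither by type of withdrawal: "Study treatment must be discontinued, and no further assessments conducted. Further attempts to contact the patient are not allowed unless safety findings require communication". The exception for safety findings also covers follow-up. Later the section leaves the handling of early withdrawals from treatment to the SAP, so a drug-only withdrawal is within its scope.

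Other sections treat the patient who stops only the drug quite differently:

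- **5.6.1** continues follow-up for OS after the drug is stopped.
- **9.2** recognises voluntary withdrawal from study drug as its own situation and states: "Patients who withdraw or are removed from the study treatment will have an EOT visit within 7 days of the decision to discontinue study drug".
- **9.3.1** schedules a 30-day visit after the last dose, with no exclusion by reason.
- **9.3.2** continues tumor assessments after any stop not due to PD, until PD or new anticancer therapy.
- **9.3.3** states: "All patients who discontinue MIRV for any reason will be followed for survival after disease progression as per Investigator", or after new therapy begins. Survival follow-up ends on consent withdrawn specifically for it; 5.7 says the same.

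Two places use an unqualified term: 5.6.2 lists withdrawal of consent as an end-of-study reason, and 5.7 stops scans when the patient withdraws consent. Neither says which consent is meant.

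In the SAP, 5.1.1 accepts a confirmatory scan after treatment discontinuation if no new therapy has begun, and 5.1.1.1 counts only confirmed responses, over all efficacy evaluable patients.

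**The concern.** Take a patient who refuses further infusions but is willing to return for scans. Section 5.6.3 tells the site to stop assessing her. Section 9 tells the site to see her within 7 days, again at 30 days, and to keep scanning and following her. A site cannot obey both, and two sites may handle the same patient differently. Because 5.6.3 is the section headed Withdrawal of Consent, it is a natural place for site staff to look.

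If 5.6.3 is followed, the analysis is affected in three ways. A first CR or PR without a repeat scan at least 28 days later is not a confirmed response, so the patient stays in the ORR denominator and leaves the numerator. DOR and PFS are censored at the last scan (SAP 5.1.1.2 and Table 3) and OS at the last date known alive (SAP 5.1.3). And if her refusal is coded as an end-of-study event under 5.6.2, SAP 5.1.1 closes the best-response window at that date.

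Patients who stop treatment may do so because of toxicity or decline. If so, the censoring is related to prognosis and the Kaplan-Meier curves would tend to look too favorable.

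**Working it through.** **Step 1: the same patient under each text.** She withdraws from treatment only, without PD.

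| Item | 5.6.3 read literally | Other sections |
|---|---|---|
| End-of-treatment visit | none | within 7 days (9.2) |
| 30-day visit | none | due (9.3.1) |
| Confirmatory scan | none | done (9.3.2) and valid (SAP 5.1.1) |
| Scans to PD or new therapy | none | continue (9.3.2) |
| Survival contact | barred unless safety requires it | continues (5.6.1, 9.3.3) |

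The texts conflict on every row. The one overlap is contact prompted by safety findings, which 5.6.3 allows.

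**Step 2: reproduce the plan's own figures.** Inputs from Protocol 10.1: n = 105, null ORR 12%, alternative 24%, one-sided target alpha 0.025. The test rejects at the smallest r with P(X ≥ r | 105, 0.12) ≤ 0.025.

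- r = 19: P = 0.0439, too large.
- r = 20: P = 0.0242, which matches the stated actual alpha.
- Power: P(X ≥ 20 | 105, 0.24) = 0.906, in line with the protocol's 91% and the SAP's 90%.
- Clopper-Pearson lower bounds: 20/105 gives 12.04% (reject) and 19/105 gives 11.26% (do not reject).

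The sample size calculation is sound. One lost response moves the observed ORR by 1/105 = 0.95 percentage points.

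**Step 3: illustrate the effect on the primary test.** The documents give no rate of treatment-only withdrawal, and none for sites that would follow 5.6.3 rather than Section 9. So let w be the assumed share of true responders who lose confirmation. The confirmed response probability is then 0.24 × (1 − w), and power is P(X ≥ 20 | 105, 0.24 × (1 − w)). The expected number of true responders is 105 × 0.24 = 25.2.

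| w | Expected responses lost (25.2 × w) | Confirmed ORR | Power |
|---|---|---|---|
| 0% | 0 | 24.0% | 0.906 |
| 2% | 0.5 | 23.5% | 0.886 |
| 5% | 1.3 | 22.8% | 0.850 |
| 10% | 2.5 | 21.6% | 0.772 |

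Only responders who refuse infusions before their response is confirmed can be lost this way.

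**Step 4: direction for the other endpoints.** Censoring at the last scan or last contact shortens follow-up. If the decision to stop is unrelated to prognosis, this costs precision but does not bias the Kaplan-Meier estimate. If patients who stop are closer to PD or death, DOR, PFS and OS are overstated. The documents hold no data from which to size this.

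**The case against.** The strongest reply is that the protocol as a whole protects this patient. Section 9.2 addresses withdrawal from study drug directly, and 9.3.1 to 9.3.3 contain no exclusion for it. Section 5.6.3 can also be read narrowly: its heading concerns consent, the order to discontinue treatment would be redundant for someone who has just refused it, and its last sentence speaks of patients who have left the study. Existing structure helps too: SAP 4.2.2 refers to separate End-of-Treatment and End-of-Study forms, and survival follow-up has its own consent.

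Much of this stands, and it rules out several stronger readings that a reader might infer:

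- **That a patient who refuses infusions necessarily loses all follow-up.** She does not under Section 9; she loses it only where a site acts on 5.6.3 literally.
- **That contact is banned outright and safety follow-up ends.** The safety exception allows contact, and 5.6.1 and 9.3.1 continue AE follow-up.
- **That 5.6.4 extends the ban to lost patients.** It classes an unreachable patient as "considered to have withdrawn from the study with a primary reason of lost to follow-up", but she has withdrawn no consent, and 5.6.2 already lists loss to follow-up as a separate reason.
- **That median DOR is overstated by a calculable amount.** Any such figure needs an invented share of progressions censored just before they occur, on an endpoint that SAP 3.11.2 does not formally test.
- **That the primary result is inflated.** A lost confirmation lowers ORR.

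The narrow reading does not remove the conflict. The opening sentence of 5.6.3 names treatment withdrawal, and nothing in the instruction that follows limits it to study withdrawal.

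**Conclusion.** The contradiction is real and should be corrected. It is an inconsistency with a risk to data completeness; it is not an error in the sample size or the test, both of which reproduce. Section 5.6.3 states a rule which, if followed, removes scans and survival follow-up that 5.6.1 and 9.2 to 9.3.3 require and a confirmatory scan that SAP 5.1.1 would accept.

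The effect on ORR is downward. The effect on DOR, PFS and OS is early censoring, with upward bias only if stopping is related to prognosis. The size is unknown. The power range of 0.886 to 0.772 is an illustration: it rests on a true ORR of 24%, on 2% to 10% of true responders losing confirmation, and on no other loss of responses.

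**What to change.** Reconcile 5.6.2, 5.6.3 and 5.7 with 9.2 to 9.3.3 by defining and recording three levels of withdrawal:

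1. **Study treatment only.** The patient follows 9.2 to 9.3.3 like any other patient who stops MIRV.
2. **Visits and scans.** Survival follow-up continues unless consent for it is also withdrawn.
3. **All follow-up.**

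Limit the stop on assessments and the contact ban to level 3, and keep the safety exception. In 5.6.2 and 5.7, say which level is meant wherever withdrawal of consent appears, so that a level 1 refusal is not coded as end of study. Section 5.6.4 needs no change.

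The cost is protocol wording and one eCRF field for the level of withdrawal. No visits are added, because the assessments are already scheduled for patients who stop MIRV, and patients keep the right to refuse everything.

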5.6.4. Lost to Follow-up

A study patient will be considered lost to follow-up if the patient repeatedly fails to return for scheduled visits and is unable to be contacted by the study site. The Investigator should make all efforts to contact the patient and to determine the patient's health status, including at least her vital status (in accordance with applicable regulations related to privacy and confidentiality). A patient should not be considered lost to follow-up until due diligence has been completed and documented. The following actions must be taken if a patient fails to return to the clinic for a required study visit:

- The site must attempt to contact the patient and reschedule the missed visit as soon as possible and counsel the patient on the importance of maintaining the assigned visit schedule and ascertain whether or not the patient wishes to and/or should continue in the study.
- In cases in which the patient is deemed lost to follow-up, the Investigator or designee must make every effort to regain contact with the patient (where possible, 3 telephone calls and, if necessary, a certified letter to the patient's last known mailing address or local equivalent methods). These contact attempts should be documented in the patient's medical record.

Should the patient continue to be unreachable, he/she will be considered to have withdrawn from the study with a primary reason of lost to follow-up.

5.7. Period of Observation

For purposes of this study, the period of safety observation extends from the time of informed consent until the 30-Day Follow-up visit unless additional follow-up safety information is requested as described in [Section 9.3](#). Short-term follow-up for patients who discontinue study drug without documented PD will be followed per RECIST 1.1 every 6 weeks (\pm 1 week) from C1D1 for the first 36 weeks then every 12 weeks (\pm 3 weeks) until PD, until the patient starts new anticancer treatment, the patient dies, or the patient withdraws consent, whichever comes first. All patients will be followed every 3 months (\pm 1 month) for survival until death, lost to follow-up, withdrawal of consent for survival or until EOS, whichever comes first.

5.8. Concomitant Medications and Procedures

All concomitant medications and supportive therapy taken within four weeks of Cycle 1, Day 1 and through 30 days after last study treatment must be recorded in the clinical database.

5.8.1. Antiemetic and Antidiarrheal Medications

An antiemetic (eg, 5-HT₃ serotonin receptor antagonists such as palonosetron, granisetron or ondansetron) medication is recommended before each MIRV dose; additional antiemetics and/or antidiarrheal (eg, loperamide) medications may be used any time at the discretion of the treating physician.

5.8.2. Folate-Containing Supplements

Folate-containing supplements should not be taken during the study.

5.8.3. Antineoplastic Therapy

All non-study related antineoplastic therapy, including but not limited to cytotoxic, immunotherapy, and VEGF-targeted therapy, is prohibited while on study drug.

5.8.4. Hematopoietic Growth Factors

Patients receiving recombinant erythropoietin (EPO) or darbepoetin- α before study start may continue to receive pretreatment doses.

The use of erythropoietic and granulocyte growth factors in accordance with ASCO guidelines may be implemented at the discretion of the treating physician.

5.8.5. Anticoagulants

The use of anticoagulant agents is allowed. Please see [Section 5.8.8](#) if using apixaban and rivaroxaban due to CYP3A interaction potential.

5.8.6. Methods of Contraception

Women of childbearing potential must agree to use highly effective contraceptive method(s) while on study drug and for at least 3 months after the last dose of MIRV. A woman of childbearing potential is a woman who is considered fertile, following menarche and until becoming post-menopausal unless permanently sterile. Permanent sterilization methods include hysterectomy, bilateral salpingectomy and bilateral oophorectomy.

The following birth control methods may be considered highly effective (failure rate of less than 1% per year):

- Combined (estrogen and progesterone) hormonal contraception associated with inhibition of ovulation
 - Oral
 - Intravaginal

- Transdermal
- Progesterone-only hormonal contraception associated with inhibition of ovulation:
 - Oral
 - Injectable
 - Implantable
- Intrauterine device (IUD)
- Intrauterine hormone-releasing system (IUS)
- Bilateral tubal occlusion
- Vasectomized partner
- Sexual abstinence

Abstinence (relative to heterosexual activity) can be used as the sole method of contraception if it is consistently employed as the patient's preferred and usual lifestyle and if considered acceptable by local regulatory agencies and Institutional Review Board/Independent Ethics Committee (IECs /IRBs). Periodic abstinence (eg, calendar, ovulation, symptom-thermal, post-ovulation methods, etc) and withdrawal are not acceptable methods of contraception.

If a contraceptive method listed above is restricted by local regulations/guidelines, then it does not qualify as an acceptable method of contraception for patients participating at sites in this country/region.

Patients should be informed that taking the study medication may involve unknown risks to the fetus (unborn baby) if pregnancy were to occur during the study. To participate in the study WCBP must adhere to the contraception requirement (described above) from the day of study medication initiation (or 14 days before the initiation of study medication for oral contraception) through the duration of study treatment and for at least 3 months after the last dose of MIRV. If there is any question that a WCBP will not reliably comply with the requirements for contraception, that patient should not be entered into the study.

5.8.7. Other Concomitant Medications

Medications for the treatment of AEs or cancer symptoms (eg, packed red blood cells and pain medications), are allowed. Prophylactic use of steroids and/or antihistamines will be considered if needed. Additionally, medications (not addressed above) used to treat underlying medical conditions at study entry including antiemetics and antidiarrheals will be allowed to continue.

5.8.8. Medications that are CYP3A or MDR1 Substrates or CYP3A Substrates with Narrow Therapeutic Index

In vitro metabolism studies demonstrated that DM4 is predominantly metabolized by thiol S-methyltransferase (TMT) to form S-methyl DM4, which is further metabolized into sulfoxide-methyl-DM4. As S-methyl DM4 has been shown to be primarily metabolized by CYP3A, its

exposure could potentially be increased in the presence of strong CYP3A inhibitors. Drinking greater than one serving (250 mL) of grapefruit juice per day should be avoided.

Both DM4 and S-methyl DM4 are substrates for MDR1 efflux transporter. Their exposure could potentially increase in the presence of MDR1 efflux transporter. In vitro metabolism data also indicates that DM4 is a time-dependent inhibitor of CYP3A4. The risk of a significant in vivo drug-drug interaction caused by inhibition of CYP3A4 or MDR1 is unknown. Treatment of patients with concomitant medications that are inhibitors of MDR1, sensitive substrates of CYP3A or are CYP3A substrates with a narrow therapeutic index should be used with caution and carefully monitored ([Appendix D](#)).

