- 11. Patients with a history of cirrhotic liver disease (Child-Pugh Class B or C)

12. Patients with a previous clinical diagnosis of noninfectious interstitial lung disease (ILD), including noninfectious pneumonitis
13. Patients requiring use of folate-containing supplements (eg, folate deficiency)
14. Patients with prior hypersensitivity to monoclonal antibodies (mAb)
15. Women who are pregnant or breastfeeding
16. Patients who received prior treatment with MIRV or other FR α -targeting agents
17. Patients with untreated or symptomatic central nervous system (CNS) metastases
18. Patients with a history of other malignancy within 3 years prior to enrollment
Note: patients with tumors with a negligible risk for metastasis or death (eg, adequately controlled basal-cell carcinoma or squamous-cell carcinoma of the skin, or carcinoma in situ of the cervix or breast) are eligible
19. Prior known hypersensitivity reactions to study drugs and/or any of their excipients

Prohibited Concomitant Medications:

Any non-study anticancer agents, including but not limited to antineoplastic agents, biologics, mAbs, and hormonal therapy, or palliative RT during study treatment.

Investigational Product, Dosage and Mode of Administration:

Patients will receive MIRV 6 mg/kg AIBW Q3W.

Duration of Study Participation:

The duration of study participation for each patient extends from the signing of the ICF until the final follow-up study visit, termination from study, death, or withdrawal of consent.

Study Committees:

An Independent Data Monitoring Committee (IDMC) will not be utilized in this open-label, single-arm study of MIRV.

Table 2: Schedule of Assessments

Procedure	Pre-screening	Screening	Cycle 1 C=3 weeks		C2+	C3	EOT	30-Day Follow-up	Survival Follow-up
			D1	D8	D1	D8	≤ 7d from discon.	30 (+14) days from last dose	Every 3 months (±1 month) from EOT
Pre-screening Informed Consent	•								
Informed Consent		• ^a							
Eligibility		• ^a							
Demographics		• ^a							
Medical History		• ^a							
Confirm Disease Diagnosis/Current Stage		• ^a							
12-Lead ECG		• ^b	• ^b						
Coagulation (PT or INR/aPTT)		• ^c							
Urinalysis		• ^c							
FFPE archived tumor tissue and/or new biopsy ^d	•								
Physical Examination ^e		• ^c	• ^f		•		•	•	
Weight		• ^c	•		•		•	•	
Vital signs ^g		• ^c	•		•		•	•	
ECOG PS		• ^c	• ^f		•		•	•	
Hematology and Chemistry ^h		• ^c	• ^f		•		•	•	

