1.5.2. Pharmacology

Results of nonclinical pharmacology studies demonstrate the following:

- FR α has limited normal tissue expression and marked expression in solid tumors, particularly cancers of the ovary and endometrium ([Investigator Brochure](#)). In vitro studies demonstrated that MIRV binds cell surface FR α with high apparent affinity (≤ 0.1 nM) and shows potent ($IC_{50} \leq 1$ nM) and selective cytotoxicity against cells expressing FR α . MIRV-mediated cytotoxicity involves binding, internalization, and degradation of MIRV, which releases DM4. DM4 can be methylated to yield S-methyl-DM4. Both DM4 and S-methyl-DM4 can inhibit tubulin polymerization and microtubule assembly, causing cell death. The lipophilic molecules S-methyl DM4 and DM4 can also diffuse to neighboring cells and induce bystander killing.
- In vitro cytotoxicity studies suggest that cells sensitive to MIRV express higher levels of FR α and release 10- to 100-fold more cytotoxic maytansinoid than cells resistant to MIRV.
- MIRV retains the inherent activities of its Ab moiety, M9346A, including binding affinity (apparent affinity ≤ 0.1 nM) and selectivity for FR α , capacity for uptake, internalization and degradation by FR α -positive target cells, and ability to induce Ab-dependent cell-mediated cytotoxicity (ADCC) in vitro.
- MIRV demonstrates significant activity against FR α -positive xenografts. Partial and/or complete regressions in xenograft models of EOC were seen at doses of MIRV well below its maximum tolerated dose (MTD).

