APPENDIX D. LIST OF CONCOMITANT MEDICATIONS REQUIRING CAREFUL MONITORING

CYP Enzymes	Sensitive Substrates	Substrates with Narrow Therapeutic Range
CYP3A	Alfentanil, aprepitant, budesonide, buspirone, conivaptan, darifenacin, darunavir, dasatinib, dronedarone, eletriptan, eplerenone, everolimus, felodipine, indinavir, fluticasone, lopinavir, lovastatin, lurasidone, maraviroc, midazolam, nisoldipine, quetiapine, saquinavir, sildenafil, simvastatin, sirolimus, tolvaptan, tipranavir, triazolam, vardenafil	Alfentanil, astemizole, cisapride, cyclosporine, dihydroergotamine, ergotamine, fentanyl, pimozide, quinidine, sirolimus, tacrolimus, terfenadine

Ref: FDA drug development resources:

(<http://www.fda.gov/drugs/developmentapprovalprocess/developmentresources/druginteractionslabeling/ucm093664.htm#classSub>).

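### Protocol 5.8.8 warns that strong CYP3A inhibitors may raise S-methyl DM4 exposure, but its caution instruction and Appendix D leave them out

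*Protocol*

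**What the plan says.** Protocol section 5.8.8 describes interactions in two directions.

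- **Other drugs acting on the payload.** S-methyl DM4 is mainly metabolized by CYP3A, so its "exposure could potentially be increased in the presence of strong CYP3A inhibitors". A daily limit on grapefruit juice follows. DM4 and S-methyl DM4 are also MDR1 substrates, and here the text reads "Their exposure could potentially increase in the presence of MDR1 efflux transporter".
- **The payload acting on other drugs.** In vitro, DM4 is a time-dependent inhibitor of CYP3A4.

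The section then states that "The risk of a significant in vivo drug-drug interaction caused by inhibition of CYP3A4 or MDR1 is unknown". It closes with its only instruction on co-administered drugs, which asks for caution and careful monitoring and cites Appendix D. The instruction applies to "Treatment of patients with concomitant medications that are inhibitors of MDR1, sensitive substrates of CYP3A or are CYP3A substrates with a narrow therapeutic index".

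Appendix D has a single enzyme row, CYP3A, and two drug columns. One is for sensitive substrates and the other is headed "Substrates with Narrow Therapeutic Range".

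Two other places bear on the point. The prohibited-medication text in the Synopsis covers "Any non-study anticancer agents, including but not limited to antineoplastic agents, biologics, mAbs, and hormonal therapy", together with palliative radiotherapy. Section 5.8.7 states that "medications (not addressed above) used to treat underlying medical conditions at study entry including antiemetics and antidiarrheals will be allowed to continue".

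**The concern.** The hazard statement and the instruction do not match. The section identifies strong CYP3A inhibitors as a possible cause of higher S-methyl DM4 exposure, yet its action sentence does not mention them. The appendix that sites would consult when checking a medication list has no place for them either.

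S-methyl DM4 is not an inert breakdown product. Section 1.5.2 says "Both DM4 and S-methyl-DM4 can inhibit tubulin polymerization and microtubule assembly, causing cell death". Section 5.5.2.1 reports a relationship between MIRV plasma exposure and ocular events, and gives limiting that risk as part of the reason for the 6 mg/kg dose. That relationship is for MIRV and not specifically for S-methyl DM4, but it shows that the programme treats exposure as relevant to safety.

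At stake is whether a site reviewing a patient's medications is prompted to question, replace or watch a strong CYP3A inhibitor. As written, the instruction gives no such prompt.

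**Working it through.** The plan states no figure to reproduce. The check sets section 5.8.8 against Appendix D and then looks for a rule elsewhere.

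**Step 1. Classes raised, and where each is carried through.**

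| Class raised as a concern in 5.8.8 | Direction | In the caution sentence | Column in Appendix D |
|---|---|---|---|
| Strong CYP3A inhibitors | raise S-methyl DM4 | No | No |
| MDR1 inhibitors | raise DM4 and S-methyl DM4 | Yes | No |
| Sensitive CYP3A substrates | may be raised by DM4 | Yes | Yes |
| Narrow-index CYP3A substrates | may be raised by DM4 | Yes | Yes |

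The caution sentence covers 3 of 4 classes; Appendix D has a column for 2 of 4. Both classes without a column are those that could raise payload exposure.

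**Step 2. Content of Appendix D.** The sensitive-substrate column has 30 entries and the narrow-range column 12, so 30 + 12 = 42 entries. Alfentanil and sirolimus appear in both, so 42 − 2 = 40 distinct drugs. No entry stands under an inhibitor heading, and there is no MDR1 row. This counts headings. It does not show that none of the 40 drugs has inhibitor activity, because the documents do not classify them that way.

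**Step 3. The MDR1 sentence.** It says that exposure could rise when the transporter is present. The caution sentence in the same paragraph refers to MDR1 inhibitors, so the intended meaning can be recovered. This is a wording error.

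**Step 4. Search for a rule elsewhere.**

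- Sections 3.1.1 and 3.1.2 (eligibility) have no criterion on CYP3A inhibitors.
- The Synopsis prohibited-medication text and section 5.8.3 concern anticancer treatment only.
- Section 5.8.7 permits existing medications that the preceding subsections have not addressed, and none of those subsections addresses CYP3A inhibitors.
- Section 5.8.5 sends users of apixaban and rivaroxaban to 5.8.8 because of CYP3A. Neither drug is named there or in Appendix D.
- Section 5.8.8 does not refer the reader to the Investigator Brochure on this point; it cites only Appendix D.

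The only specific advice tied to the CYP3A-inhibitor warning is therefore the grapefruit-juice limit, which concerns a drink and gives no direction on prescribed inhibitors.

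**The case against.** The strongest reply is that a prescriber who reads 5.8.8 is told of the hazard. The warning stands a few sentences above the instruction, and the sentence just before the instruction mentions inhibition of CYP3A4. On this view one phrase is missing and the intent is plain. General safeguards also apply to everyone: co-medications are recorded (5.8), laboratory results are reviewed before each dose (7.10), ocular symptoms are assessed before each cycle (7.9.1), doses are held, reduced or stopped for toxicity (5.5), and free DM4 and S-methyl DM4 are measured (6.1). The protocol calls the in vivo risk unknown, and nothing shows that harm would follow.

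Much of this stands. Monitoring as such is not missing, and no consequence has been quantified. The count of four classes is a reading of the section's concerns; the section title also names MDR1 substrates, which the text does not develop as a hazard. MDR1 inhibitors already carry the caution instruction, so their missing list is mainly a matter of convenience. The MDR1 wording slip would not merit a comment alone. The anticoagulant pointer is not broken, because the caution works by class. The 5.8.7 permission shows only that no other rule fills the gap, since the classes that do receive caution are also permitted. The statement in 5.9.1 that no antidote is known concerns overdose and is only background here.

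The main point survives. The same unknown risk was judged enough to ask for caution with MDR1 inhibitors, and no reason is given for treating strong CYP3A inhibitors differently. The general safeguards mostly detect toxicity once it has occurred and do not prompt a site to look at the inhibitor. Sampling is sparse and concentrations are only summarized (protocol 10.2, SAP section 9). Section 6.1 allows extra samples for treatment-related serious events, but no use of concentrations to manage an individual patient's co-medication is described.

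**Conclusion.** The concern holds as a gap in the safety instructions. Section 5.8.8 flags strong CYP3A inhibitors and then omits them from its only instruction on co-administered drugs, and neither Appendix D nor any other part of the protocol supplies the rule. The missing inhibitor-specific caution carries the point; the absent MDR1 list, the transporter wording and the anticoagulant entry are secondary.

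Its clinical size cannot be stated. The documents give no rate of strong-inhibitor use and no estimate of the exposure change. The conclusion rests on two assumptions: that sites act on the instruction and its list more than on the explanatory text above it, and that the protocol's own statement about CYP3A metabolism is right. Sample size, type I error, power and the planned analyses are unaffected. The change is worth making on safety grounds.

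**What to change.** 1. Add strong CYP3A inhibitors to the caution sentence in section 5.8.8, and widen the section title so that it covers inhibitors.
2. Add strong CYP3A-inhibitor and MDR1-inhibitor entries to Appendix D. The drug names must come from a current reference source, since the protocol does not list them.
3. Reword the MDR1 sentence to say that exposure could rise when an MDR1 inhibitor is given.
4. Keep the cross-reference in section 5.8.5. Optionally name apixaban and rivaroxaban in Appendix D so that the pointer ends at a listed drug.

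The cost is an amendment to one section and one appendix table, a notice to sites, and slightly more checking of medication lists. Section 12.7 requires written ethics approval for protocol changes, and the Synopsis plans approximately 98 centers, so the administrative load is real. Making the edit with the next amendment would limit it. No visit, procedure or analysis changes.
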